## Objectives

The primary objective of the study is to assess the efficacy of CC-93538 versus placebo in obtaining histologic improvement based on tissue eosinophil (eos) count in EGE at Week 16.

The secondary objectives are:

- To assess the efficacy of CC-93538 versus placebo in reducing EGE-related symptoms at Week 16
- To assess the efficacy and the persistence of effect of CC-93538 versus placebo at 48 weeks in:
  - Obtaining histologic improvement based on tissue eos count in EGE
  - Reducing EGE-related symptoms
- To assess the persistence of effect of CC-93538 through administration of a less frequent dosing regimen at 48 weeks in:
  - Obtaining histologic improvement based on tissue eos count in EGE
  - Reducing EGE-related symptoms
- To evaluate the safety and tolerability of CC-93538 including characterization of the immunogenicity profile
- To evaluate the efficacy and the persistence of effect of CC-93538 versus placebo for 48 weeks in reducing concomitant corticosteroid use
- To evaluate the time to and frequency of EGE flare events and use of rescue therapy during the study
- To assess trough concentrations of CC-93538 in subjects with EGE

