## **7.3 Method of Treatment Assignment**

### **7.3.1 The Induction Phase and the Maintenance Phase**

Subjects enrolled in the Induction Phase will be centrally randomized on Day 1 after all screening and baseline assessments have been completed and the investigator has verified that the subject is eligible per the inclusion ([Section 4.2](#)) and exclusion criteria ([Section 4.3](#)). Subjects will be randomized 2:1 to receive active CC-93538 treatment (360 mg SC weekly for 16 weeks) or matching placebo for 16 weeks. Treatment assignment at baseline will be stratified by (with/without) concomitant use of corticosteroid treatment at baseline (up to 10 mg/day as the equivalent of prednisone) to ensure an equal balance in the treatment arms. Randomization will be performed through the Interactive Web Response System (IWRS) system.

Subjects enrolled in the Maintenance Phase will be centrally re-randomized on Week 16 (the completion of Induction Phase). Subjects who randomized to receive CC-93538 360 mg SC once weekly in the Induction Phase will be re-randomized 1:1 to receive active CC-93538 treatment (360 mg SC once weekly or 360 mg SC once every other week), and subjects who randomized to receive matching placebo in the Induction Phase will continue placebo. Re-randomization will also be performed through the IWRS system.

Treatment groups are described in [Section 7.2](#). The treatment each subject will receive will not be disclosed to the investigator, study center personnel, subject, Sponsor, or their representatives. The treatment codes will be held according to the IWRS. Further instructions will be provided in a separate IWRS manual.

The study blind should be maintained for persons responsible for the ongoing conduct of the study (after all subjects have completed the Week 48 assessments for endpoint analysis). Blinded persons may include but are not limited to: Clinical Research Physician (also referred to as Clinical Trial Physician), Clinical Research Scientist, Clinical Trial Manager, Study Statistician, Data Manager, Programmers, and Clinical Research Associates. For details of the emergency procedure for unblinding of individual subjects, see [Section 11.4](#).

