### **9.3 Sample Size and Power Considerations**

The sample size is based on two-sample t-test for the primary endpoint, changes in mean number of peak eos per hpf in GI biopsies from baseline to Week 16. The null hypothesis and the alternative hypothesis for the primary endpoint are as follows;

- Changes in mean number of peak eos from baseline at Week 16

Null hypothesis  $H_0: \mu_{CC-93538} = \mu_{Placebo}$

Alternative hypothesis  $H_a: \mu_{CC-93538} \neq \mu_{Placebo}$ ,

where  $\mu_{CC-93538}$  represents the true mean change value relative to CC-93538 and  $\mu_{Placebo}$  represents true mean change value relative to placebo.

Using this hypothesis, if the expected mean change in eos count in the active treatment group was -70, the expected mean change in eos count in the placebo group was 0, and the standard deviation (SD) was 70, the sample size necessary to achieve at least 80% power in a t-test at a significance level of 0.05 was calculated. Using a 2:1 ratio of active to placebo, 39 subjects are required. Assuming a Week 16 drop-out rate of approximately 10%, the goal is to enroll a total of 45 subjects.

The expected change from baseline in eos count in the active treatment group is based on the Phase 2 EoE study (Study RPC02-201); mean value at baseline for the CC-93538 360 mg treatment group of 139.4, and mean value at Week 16 of 31.3, with a percent change of approximately 80%. The baseline value in patients with EGE was assumed to be approximately 90 based on the results of studies of other drugs in patients with EGE (Dellon, 2020). Therefore, the expected change from baseline in eos in the active treatment group is assumed to be approximately 70. Change from baseline in eos count in the placebo group was assumed to be 0 based on the results of studies of other drugs (Dellon, 2020). With reference to the baseline GI eos count results of other drug studies of 52 (Dellon, 2020), the results of Study RPC02-201 in the CC-93538 360 mg group of 90, and the results of Study RPC02-201 in the CC-93538 180 mg group of 71, SD was assumed to be 70, which is approximately the mean of those values.

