#### **9.6.1.2 Changes in Mean Number of Peak eos Count from Baseline to Week 16 (Induction Phase)**

The primary analysis will be conducted on the ITT population based on an analysis of covariance (ANCOVA) model with treatment group, concomitant steroid use (yes or no), and baseline eos count included in the model. The comparison between CC-93538 360 mg SC once weekly and placebo for change in number of peak eos count from baseline at Week 16 will be made using the difference in least squares mean (LSM) at a 5% 2-sided significance level. Point estimates for the mean difference between the two treatment groups using the LS mean changes and corresponding 95% Wald CI will be reported. In addition, LSMs (standard error [SE]), arithmetic means (SD), and arithmetic mean changes (SD) will be summarized by treatment group.

Missing data will be handled using a multiple imputation (MI) approach under a missing at random (MAR) assumption.

Sensitivity analyses will be performed to support the primary analysis and provide additional insights to understand the treatment effect. For the primary estimand analysis, robustness due to missing data MI under MAR assumption will be explored using tipping point analysis ([Yan, 2009](#); [Campbell, 2011](#); [Yuan, 2014](#)). In considering the ICEs of study interest (ie, ICE number 2, use of rescue therapy/prohibited medication, and ICE number 3, treatment discontinuation followed by use of rescue therapy/prohibited medication), an analysis using the hypothetical estimand strategy for change in eos count at Week 16 will be conducted.

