### **9.6.3 Analysis of Secondary Efficacy Endpoints**

#### **9.6.3.1 Analyses Methods**

##### Continuous variables:

- Changes in mean number of peak eos count per hpf from baseline to Week 48
- Changes from baseline in each of 5 domain scores of the Izumo Scale (Weeks 14, 16, 32, and 48)
- Changes from baseline in total score of EGID Severity Score (Weeks 16, 32, and 48)
- Percent changes in mean number of peak eos per hpf in GI biopsies from baseline (Weeks 16 and 48)
- The time until concomitant corticosteroid treatment to zero (and continued by Week 48) (from Week 16 through Week 48)

The analysis for continuous variables of the secondary endpoints will be conducted on the ITT population using the ANCOVA model with treatment group (CC-93538 360 mg SC once weekly, CC-93538 360 mg SC once every other week, and placebo), prior steroid use (yes or no), and baseline values included in the model. Point estimates for the mean difference between the treatment groups using the LS mean changes and corresponding 95% Wald CI will be reported. The transition from the Maintenance Phase to the OLE Phase will be treated as ICE. Missing data and ICEs will be handled via the same strategy as for the primary analysis.

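### The Week 48 model omits the Week 16 value, the natural baseline for weekly versus every-other-week dosing, so that small nominal contrast gives up precision at no need

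*Combined protocol and SAP*

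**What the plan says.** Section 7.3.1 randomises subjects 2:1 on Day 1, stratified by corticosteroid use at baseline. At Week 16 the CC-93538 subjects are re-randomised 1:1 to weekly or every-other-week dosing, and placebo subjects stay on placebo. On the mechanics of the second step it says "Re-randomization will also be performed through the IWRS system" and leaves further instructions to an IWRS manual. It attaches no stratification factor to that step, nor do Sections 3.1.3, 6.2 and 7.2.2 or the footnotes to Table 5.

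For the Week 48 endpoints, Section 9.6.3.1 says: "The analysis for continuous variables of the secondary endpoints will be conducted on the ITT population using the ANCOVA model with treatment group". The treatment term has three levels (weekly, every other week, placebo). The covariates are steroid use, here called prior use although Section 9.6.1.2 calls it concomitant use, and baseline values. Section 6 and Table 4 place baseline on Day 1 before dosing. For biopsies it is the screening EGD, because Table 4 schedules none on Day 1. There is no Week 16 term. The section reports LS mean differences between the treatment groups, so weekly versus every other week is among the estimates produced. It gives every comparison other than the primary a nominal p-value.

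The secondary objective concerned is "To assess the persistence of effect of CC-93538 through administration of a less frequent dosing regimen at 48 weeks in" histologic improvement and symptom reduction.

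**The concern.** The two active regimens are identical up to Week 16 and are randomised there. For the contrast between them, the Week 16 value is therefore a true baseline: it is measured under common treatment, before the regimens diverge, and it is probably closer to the Week 48 outcome than the Day 1 value is. The planned model adjusts for a value at least 16 weeks older and leaves this one out.

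The contrast is small and has no stated power or precision target, but it has a use. Sections 3.1.4 and 7.2.3 allow the open-label regimen to be revised after the results are available. At most about 30 subjects inform the comparison of the two regimens. Chance differences in how well the arms had already responded at Week 16 are then a sizeable part of the noise, and a measured covariate could remove some of it.

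**Working it through.** **1. The plan's own figure.** Section 9.3 says "the sample size necessary to achieve at least 80% power in a t-test at a significance level of 0.05 was calculated", with changes of -70 and 0 and an SD of 70, so d = 70/70 = 1. On the SD it says "SD was assumed to be 70, which is approximately the mean of those values"; the mean is (52 + 90 + 71)/3 = 71. It concludes: "Using a 2:1 ratio of active to placebo, 39 subjects are required". Noncentral-t power at two-sided 0.05 is 78.5% for 24 + 12 = 36 and 81.8% for 26 + 13 = 39, so 39 reproduces. Dropout gives 39/0.9 = 43.3, hence 44, and 45 is the next multiple of 3. None of this addresses weekly versus every other week.

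**2. How many are re-randomised.** Section 3.1.2 puts about 30 on active treatment. With 10% dropout, 30 x 0.9 = 27 remain, and the exclusions in Section 6.4.2.11 can reduce this further. The working range is 15 + 15 (a ceiling) to 14 + 13.

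**3. Chance imbalance at Week 16.** In SD units the difference between arm means has standard error sqrt(1/n1 + 1/n2), and P(at least 0.5 SD) = 2[1 - Phi(0.5/SE)].

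| Arms | SE (SD units) | SE at SD 70 (eos/hpf) | P(at least 0.5 SD) |
|---|---|---|---|
| 15 / 15 | 0.365 | 25.6 | 17% |
| 14 / 13 | 0.385 | 27.0 | 19% |
| 13 / 13 | sqrt(2/13) = 0.392 | 70 x 0.392 = 27.5 | 20% |

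**4. What passes into Week 48.** With equal residual SDs at the two visits, the expected shift is rho x imbalance, where rho is the partial correlation of Week 16 with Week 48 given baseline. The documents give no rho; 0.3 to 0.7 is assumed. A 0.5 SD imbalance is 0.5 x 70 = 35 eos/hpf, of which 0.3 x 35 = 10.5 to 0.7 x 35 = 24.5 carries over. Over all re-randomisations at 15 / 15, the carried-over part has SD 7.7, 12.8 or 17.9 for rho 0.3, 0.5 or 0.7, against 25.6 for the imbalance itself.

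**5. Gain from adjustment.** Half-width = t x 70 x sqrt(1 - rho^2) x sqrt(1/n1 + 1/n2), with t on n1 + n2 - 4 degrees of freedom.

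| Arms | rho = 0 (no gain) | 0.3 | 0.5 | 0.7 |
|---|---|---|---|---|
| 15 / 15 | 52.5 | 50.1 | 45.5 | 37.5 |
| 14 / 13 | 55.8 | 53.2 | 48.3 | 39.8 |

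The variance ratio 1 - rho^2 is 0.91, 0.75 or 0.51, equivalent to 1.10, 1.33 or 1.96 times the sample size. The calculation ignores the degree of freedom spent on the extra covariate. It also ignores the extra residual degrees of freedom that placebo subjects bring to the planned three-group model.

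**6. Validity check by simulation.** The setting was 15 per arm, no true difference and 20,000 runs, with baseline correlated 0.3 with both later values and simple Week 16 to Week 48 correlations of 0.3, 0.5 and 0.7. By (r - 0.09)/0.91 these correspond to partial correlations of 0.23, 0.45 and 0.67. Type I error was 4.9% to 5.1% with and without the Week 16 covariate, and mean estimates were within 0.2 eos/hpf of zero. Mean half-widths went from 50.4 to 50.1, 50.5 to 46.0 and 50.6 to 38.3. At the weakest correlation the gain is therefore close to nil.

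**The case against.** The strongest reply is that nothing in the plan is invalid. That stands. Four stronger readings are tempting, and the documents do not support them.

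- *The re-randomisation is unstratified.* This would be inferred from silence. Section 9.1 names concomitant steroid use as the stratification factor without limiting it to Day 1, and the IWRS manual is a separate document. One can say only that no factor is stated for this step.
- *The model adjusts for nothing but the original baseline.* Steroid use is also in it.
- *Imbalance passes whole into the Week 48 contrast and biases it.* Only rho times the imbalance passes. The estimate is unbiased over re-randomisations, the error rate holds, and the interval already allows for chance imbalance.
- *Every re-randomised subject has a Week 16 value.* Section 6.2.1 allows the Week 16 EGD to be omitted when a flare EGD was too recent, and Section 3.1.6 sends subjects with mild to moderate flares on to Maintenance. Weekly Izumo entries can be missed too.

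The inferential status is also modest. The contrast is nominal, the objective does not say versus weekly, and for binary endpoints the interval specified in Section 9.6.3.1 is against placebo only. Section 9.1 leaves further analysis detail to a SAP whose text is not in the combined document, so a Week 16 term could be specified there. These points limit the importance of the matter; they do not argue against the covariate.

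**Conclusion.** The point holds as an inexpensive improvement, not as the correction of an error. As written in Section 9.6.3.1, the Week 48 model leaves out the one covariate that is the actual pre-randomisation baseline for the between-regimen contrast. The imbalance probabilities of 17% to 20% need only the arm sizes and approximate normality. The gain depends on the unknown partial correlation: over 0.3 to 0.7, the half-width at 15 per arm falls from 52.5 to between 50.1 and 37.5 eos/hpf.

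The SD of 70 is borrowed from Section 9.3, which does not give it for Weeks 16 and 48 on active treatment. With an assumed baseline near 90 and a fall of about 70, the expected Week 16 mean is about 90 - 70 = 20, so the spread then may be smaller. Every eos/hpf figure scales with the SD (at an SD of 35 each halves), while the percentages and variance ratios do not change.

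**What to change.** For the nominal weekly versus every-other-week contrast at Week 48, pre-specify a separate ANCOVA in re-randomised subjects only. Its terms are regimen, steroid use, original baseline and the Week 16 value of the same endpoint. Handle any missing Week 16 value, such as an EGD omitted under Section 6.2.1, with the multiple imputation already planned in Section 9.6.1.2 and carried into Section 9.6.3.1. Restricting the model to re-randomised subjects also settles who belongs in it, because CC-93538 subjects who never enter Maintenance were never assigned to either maintenance regimen.

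Leave the comparisons with placebo as planned: there Week 16 is post-treatment, and adjusting for it would remove part of the effect being estimated. The primary analysis and the randomisation need no change.

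The cost is one additional model and one sentence on missing covariates, written before the primary database lock that Section 9.1 sets after Week 48. It needs no new data or visits.

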### **7.3.2 The OLE Phase**

After all OLE baseline assessments have been completed, all eligible subjects will be assigned to the same IP and will receive open-label CC-93538 360 mg SC starting on OLE Day 1 and once weekly throughout the OLE Phase.

## **7.4 Packaging and Labeling**

### **7.4.1 The Induction Phase and the Maintenance Phase**

The label(s) for IP will include Sponsor name, address and telephone number, the protocol number, IP name, dosage form and strength (where applicable), amount of IP per container, lot number, expiry date (where applicable), medication identification/kit number, dosing instructions, storage conditions, and required caution statements and/or regulatory statements as applicable. Additional information may be included on the label as applicable per local regulations. For the PFS presentation, a label cover on the active and placebo syringes will be used to maintain the blind.

#### **7.4.2 The OLE Phase**

The label(s) for IP will include Sponsor name, address and telephone number, the protocol number, IP name, dosage form and strength (where applicable), amount of IP per container, lot number, expiry date (where applicable), medication identification/kit number, dosing instructions, storage conditions, and required caution statements and/or regulatory statements as applicable. Additional information may be included on the label as applicable per local regulations.

#### **7.5 Investigational Product Accountability and Disposal**

Celgene (or designee) will review with the investigator and relevant site personnel the process for IP return, disposal, and/or destruction including responsibilities for the site versus Celgene (or designee).

All supplies of IP and placebo will be accounted for in accordance with GCP. There will be an individual IP accountability record for each subject and the investigator should maintain accurate records relating to IP supplies received during the study. These records should include the amount of and dates clinical drug supplies were received, dispensed and administered to the subject by the investigative site or by a home healthcare nurse, or returned by the designated investigative site staff or by a home healthcare nurse and returned to the Sponsor. If errors or damages in the clinical drug supply shipments occur, the investigator should contact the IP supplier and the Study Monitor immediately. Copies of the IP accountability records will be provided by each investigator for inclusion in the Trial Master File after database lock. The Study Monitor will periodically check the supplies of IP held by the investigator or pharmacist to verify accountability of all IP used.

The investigator will provide IP only to the identified subjects of this study, according to the procedures described in this study protocol. After the end of the study, the Study Monitor will ensure that all unused IP and all medication containers, as applicable, can be destroyed on-site as long as proper documentation is supplied. If destruction on-site is not possible then any unused medication and containers, as applicable, will be returned to the Sponsor or designee. The Study Monitor will perform final accountability, package, seal and prepare for shipment. The contract research organization will verify that a final report of drug accountability is prepared and maintained in the investigator Trial Master File.

#### **7.6 Investigational Product Compliance**

The investigator must ensure that the IP will be used only in accordance with the protocol and that subjects are correctly instructed on how to take their IP and that each subject is fully compliant with their assigned dosage regimen. Investigational product non-compliance is defined as taking less than 80% or more than 120% of IP doses during the study. Records of IP used and intervals between visits will be kept during the study. Drug accountability will be noted by the field monitor during site visits and at the completion of the study. The IP should be dispensed by the investigator, or by a qualified individual under the investigator's supervision. An up-to-date treatment inventory/dispensing record must be maintained.

## 8 CONCOMITANT MEDICATIONS AND PROCEDURES

There are specific requirements for cessation of medication use prior to enrollment, as stated in the exclusion criteria ([Section 4.3](#)). All treatments (including prescription and over the counter medications, herbal and dietary supplements, dietary modifications, vaccines, and procedures) used by subjects within the 4 weeks (28 days) prior to the first Screening Visit or at any time during the study in addition to the IP are regarded as prior or concomitant treatments and must be documented on the appropriate section of the eCRF. In addition, a history of previous treatments for EGE will be documented. The investigator must document all treatments received at the time of the EGD (for any indication) through Day 1.

All concomitant treatments, including blood and blood products, used from 28 days prior to the first Screening Visit until 16 weeks after the last dose of IP or until the Final Safety Follow-up Visit, whichever is longer, must be reported on the eCRF.

### 8.1 Permitted Concomitant Medications and Procedures

Concomitant medications, dietary modifications, and procedures that are permitted during the study include the following:

- Subjects must have maintained a stable diet for at least 4 weeks prior to the first Screening Visit and must agree to maintain a stable diet throughout the Induction Phase and the Maintenance Phase. Subjects on a food elimination diet for the treatment of food allergy or EGE should maintain it without making any changes through the end of the study and should have maintained this diet for at least 4 weeks prior to the first Screening Visit. Subjects must agree to not introduce any changes in their diet while participating in the Induction Phase and the Maintenance Phase. However, following IP administration, subjects experiencing a severe EGE flare requiring a dietary modification for rescue therapy may be eligible to continue in the study according to protocol requirements. See [Section 6.4.2.10](#).
- Subjects may use systemic corticosteroids up to 10 mg/day of prednisone for EGE as a concomitant corticosteroid treatment. Stable doses/regimens must have been maintained for at least 4 weeks prior to the first Screening Visit and regimens will remain stable until Week 16 (completion of the Induction Phase). If the reduction of EGE-related symptoms is observed after Week 16 (in the Maintenance Phase and the OLE Phase), the investigator should begin tapering dosage regimen of concomitant corticosteroid treatment after Week 16. The dose reduction should be 2.5 mg/week (as the equivalent of prednisone).
- Subjects may use inhaled corticosteroids, proton pump inhibitors (PPIs), leukotriene receptor antagonists (eg, montelukast), or mast cell stabilizers (eg, cromolyn sodium) for indications other than EGE if on stable doses/regimens for at least 4 weeks prior to the first Screening Visit and regimens will remain stable throughout the Induction Phase and the Maintenance Phase. If one of these medications was recently discontinued, it must have been discontinued at least 4 weeks prior to the first Screening Visit.
- Subjects may use medium potency topical corticosteroids (eg, mometasone furoate cream or lotion) for dermatologic conditions if on stable doses/regimens for at least 4 weeks prior to the first Screening Visit and regimens will remain stable throughout the Induction Phase and the Maintenance Phase. If the medication was recently discontinued, it must have been discontinued at least 4 weeks prior to the first Screening Visit.

- Subjects may use intranasal corticosteroids, antihistamines, or other medications for seasonal allergies or other conditions as needed.
- Subjects may use low potency topical corticosteroids for dermatological conditions as needed.
- Subjects receiving PPIs, leukotriene receptor antagonists (eg, montelukast), or mast cell stabilizers (eg, cromolyn sodium) medication for the indication of EGE at the first Screening Visit may participate if these medications has been maintained at a stable dose from at least 4 weeks prior to the first Screening Visit through the Induction Phase and the Maintenance Phase. Subjects who discontinued these medications must not have received these medications for at least 4 weeks before the First Screening Visit and must agree not to restart these medications during the study. However, following IP administration, subjects experiencing a severe EGE flare requiring the addition of these medications or modification to these medication regimens for rescue therapy may be eligible to continue in the study according to protocol requirements. See [Section 6.4.2.10](#).
- Subjects receiving SC immunotherapy must have been on stable doses for at least 3 months prior to the first Screening Visit and for the Induction Phase and the Maintenance Phase.
- Administration of non-live vaccines including COVID-19 vaccine (except for investigational COVID-19 vaccines administered as part of a clinical trial) is allowed and may occur during the study. For COVID-19 vaccine regimens requiring more than one dose, the full series (eg, both doses of a 2-dose series) should be completed prior to enrollment when feasible, and when a delay in enrollment would not put the study participant at risk. Ideally, adverse events attributable to a vaccine should have resolved prior to enrollment.

Refer to [Table 7](#) for a summary of the timing for stable dosing regimen requirements for certain medications and requirement for a stable diet.

